7.3. Managing adverse effects of entecavir

7.3.1. Adverse effects of entecavir

- Headache, fatigue, dizziness, nausea, upper abdominal pain, upset stomach, diarrhea, vomiting, trouble sleeping or sleepiness, changes to liver and pancreas enzymes. These side effects were generally mild to moderate in severity.
- Lactic Acidosis: Patients taking drugs similar to entecavir have experienced lactic acidosis. Symptoms of lactic acidosis include weakness/tiredness, muscle pain, trouble breathing, stomach pain with nausea and vomiting, feeling cold (particularly in extremities), dizziness/lightheadedness, and increased heart rate.
- Hepatitis "flares": In patients with chronic hepatitis B, liver enzyme changes are common.
- Laboratory studies have shown that entecavir does not interact with the enzymes in the liver that are responsible for most drug interactions. However, because the body gets rid of entecavir in the urine, it is possible that drugs which affect kidney function could increase the levels of entecavir when a patient uses both drugs. These types of drugs are not allowed in this study.
- When mice and rats were given entecavir for their entire adult life, these animals developed more tumors, including cancerous tumors, than are normally expected. Male mice developed non-cancerous lung tumors when they were exposed to entecavir at levels greater than or equal to 4 times higher than participants will be exposed to in this study. Cancerous lung tumors were also observed in male and female mice when they were given high levels of entecavir. Further animal studies have been performed to better understand these findings. These additional studies suggest that the lung findings in mice are unique for mice. The lung findings in mice did not occur in rats, dogs or

monkeys. It is not known whether these tumor findings in animals are relevant to humans who are treated with Entecavir.

7.3.2. Entecavir and renal function

Entecavir dosing is based upon CrCL: Creatinine clearance will be calculated for all participants prior to initiating therapy and at each study visit to determine Entecavir dose.

- Participants whose calculated creatinine clearance decreases to <50 ml/min should have this value confirmed within 72 hrs.
- Entecavir may be continued if the CrCL is ≥30-50 ml/min at the adjusted dose of 0.5 mg every 48 hours.
- Entecavir will be discontinued if the CrCL is <30 ml/min.

7.4. Pregnancy

Participants will be asked to practice effective birth control while they are taking antiviral agents in this study. Additionally, following precautions will be taken:

- All female participants with reproductive potential will undergo pregnancy test on enrollment and will have pregnancy tests performed at each visit during treatment.
- If a participant on entecavir or peginterferon alfa-2a becomes pregnant, the study physician should be notified immediately and treatment will be discontinued immediately. Subsequent management will be at the discretion of the study physician. The study will collect data on the outcomes of any pregnancies that occur in women who conceived while taking study medication.

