4.2. Exclusion criteria

- 1. History of hepatic decompensation, including but not limited to ascites, variceal bleeding, or hepatic encephalopathy.

2. Evidence of decompensated liver disease prior to or during screening, including direct bilirubin >0.5 mg/dL, INR >1.5, or serum albumin <3.5 g/dL.
3. Platelet count <120,000/mm³, hemoglobin <13 g/dL (males) or <12 g/dL (females), absolute neutrophil count < 1500 /mm³ (<1000/mm³ for African-Americans) at the last screening visit.
4. Previous treatment with medications that have established activity against HBV including, but not limited to, interferon and nucleos(t)ide analogs ≥24 weeks. Patients with <24 weeks of prior HBV treatment and a wash-out period >24 weeks are not excluded. Brief and episodic use of famciclovir or valacyclovir for herpes infection is not exclusionary.
5. Known allergy or intolerance to any of the study medications.
6. Females who are pregnant or breastfeeding.
7. Females of childbearing potential unable or unwilling to use a reliable method of contraception during the treatment period.
8. Renal insufficiency with calculated creatinine clearance <50 mL/min at the last screening visit.
9. History of alcohol or drug abuse within 48 weeks of the baseline visit.
10. Previous liver or other organ transplantation including engrafted bone marrow transplant.
11. Any other concomitant liver disease, including hepatitis C or D. Non-alcoholic fatty liver disease (NAFLD) with steatosis and/or mild to moderate steatohepatitis is acceptable but NALFD with severe steatohepatitis is exclusionary.
12. Presence of anti-HDV or anti-HCV (unless HCV RNA negative) in serum on any occasion in the 144 weeks prior to the baseline visit.
13. Presence of anti-HIV (test to be completed within 6 weeks prior to the baseline visit).
14. Pre-existing psychiatric condition(s), including, but not limited to:
 - a. Current moderate or severe depression as determined by the study physician
 - b. History of depression requiring hospitalization within past 10 years
 - c. History of suicidal or homicidal attempt within the past 10 years
 - d. History of severe psychiatric disorders including, but not limited to schizophrenia, psychosis, bipolar disorder as determined by a study physician.

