5.1 Dosage and administration

Treatment Entecavir 0.5 mg daily orally for 48 weeks plus peginterferon alfa-2a 180 µg subcutaneously (sq) weekly during weeks 9-48 of treatment. After treatment discontinuation, follow-up off treatment will be for 48 weeks.

Participants will be instructed to take one tablet of entecavir daily on an empty stomach at least 2 hours prior to or after meals. Participants will be instructed to take 180 µg of peginterferon alfa-2a subcutaneously once weekly. The participant will be instructed to inject the peginterferon alfa-2a on the same day each week.

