5.3 Peginterferon alfa-2a

5.3.1 General description

Peginterferon alfa-2a is a covalent conjugate of recombinant alfa-2a interferon with a single branched molecule of polyethylene glycol with a molecular weight of approximately 40,000 daltons. Peginterferon alfa-2a is produced using recombinant DNA technology and contains 180 µg/1.0 mL in vial form and the same amount per 0.5 ml in a prefilled syringe. The drug must be kept refrigerated at +4C until use.

Interferon inhibits viral replication by inducing an antiviral state in cells. Interferon does not enter the hepatocyte, but rather binds to specific receptors on the cell surface, which initiates intracellular signaling that leads to rapid activation of multiple "interferon-stimulated genes" (ISGs); the encoded proteins of these genes inhibit viral replication in infected hepatocytes by multiple mechanisms (including inhibition of viral protein synthesis and breakdown of viral RNA). Peginterferon alfa-2a also has immunomodulatory activity that is thought to be important in obtaining a virological response. Steady-state serum concentrations of peginterferon alfa-2a are reached within 5 to 8 weeks using once weekly dosing. The mean terminal half-life after subcutaneous dosing is 160 hours compared to 5 hours for standard, non-peginterferon alfa-2a.

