5.3.3. Safety

As with standard alpha interferon, treatment with peginterferon alfa-2a is associated with many troublesome and occasionally serious, or even life-threatening, side effects. Dose discontinuation has been reported in 6% to 9% and dose modification in 31% to 47% of patients treated in the peginterferon alfa-2a registration trials for hepatitis B. The most frequent causes of dose adjustment were laboratory abnormalities such as thrombocytopenia or leucopenia. These side effects are particularly common in patients with advanced liver disease and hypersplenism. Peginterferon alfa-2a is absolutely contraindicated in patients with decompensated cirrhosis due to the possibility of serious infections, flares of disease and worsening decompensation.

The majority of clinical experience in the use of peginterferon alfa-2a has been in chronic hepatitis C in which peginterferon alfa-2a is combined with ribavirin. In the few studies of peginterferon in chronic hepatitis B it has appeared that side effects are less frequent than in chronic hepatitis C. The overall incidence of serious adverse events was less in studies in hepatitis B (4%-5%) than in those with hepatitis C (7% to 16%), and fewer drug withdrawals were reported (6% to 8% versus 17% to 33%, respectively) despite similar doses and durations of therapy. Depression was also less frequently reported in studies done in hepatitis B (4%) than hepatitis C (22%, $p < 0.001$).

Peginterferon alfa-2a should be avoided in patients with other serious co-morbid illnesses, including, but not limited to, coronary artery disease, cerebrovascular disease, serious autoimmune conditions and severe depression.

Pregnancy: Peginterferon alfa-2a is a Pregnancy Category C drug that has not been adequately evaluated in humans for its teratogenic effect. Standard interferon has been shown to increase the rate of abortion in Rhesus monkeys when given approximately 20 to 500 times the human weekly dose. Interferon, however, is highly species specific in its effects and animal studies may not reliably reflect the potential of side effects in humans. There have been no adequate and well-controlled studies of peginterferon alfa-2a in pregnant women. Therefore, in this study, women of childbearing potential will be enrolled only if they agree to use effective contraception during therapy and pregnancy testing will occur at every visit during the treatment phase.

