7.5. Adverse events – definition and management

7.5.1. Definitions

An adverse event (AE) is any adverse change from the participant's baseline (pre-treatment) condition, including intercurrent illness which occurs during the course of the trial, after the consent form has been signed, whether the event is considered related to treatment or not.

The modified World Health Organization (WHO) grading system will be used for grading severity of AEs. For AEs not outlined in the modified WHO grading system, study specific definitions will be identified in the Manual of Operation (MOP).

A serious adverse event is an untoward medical occurrence that results in any of the following:

1. Death
2. Is life threatening (risk of death at the time of the event)
3. Requires in-patient hospitalization or prolongation of existing hospitalization
4. Results in persistent or significant disability/incapacity
5. Congenital abnormality or birth defect

Important medical events that do not result in one of the events listed above may be considered a serious adverse event when, based upon appropriate medical judgment, they may jeopardize the participant and may require medical or surgical intervention to prevent one of the outcomes listed above.

A serious adverse event which is unexpected and is related will require expedited reporting to the DCC and the NIDDK and appropriate oversight committees or entities.

Disease related outcomes, such as the following, will not be considered to be serious adverse

events:

1. Development of HCC
2. Hepatic decompensation

Although pregnancy, overdose, cancer (excluding HCC), and potential drug induced liver injury (DILI) are not always serious by regulatory definition, these events must be handled as SAEs.

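### Contraception is required only until dosing ends at week 48, but at the protocol's own half-life peginterferon persists for about 4 more weeks (five half-lives assumed; about 2 to 6 weeks at three to seven)

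*Combined protocol and SAP*

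**What the plan says.** Three places in the protocol set how long contraception lasts, and all three stop with dosing:

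- Section 4.2, item 7 excludes women of childbearing potential who are "unable or unwilling to use a reliable method of contraception during the treatment period".
- Section 5.3.3 says that "women of childbearing potential will be enrolled only if they agree to use effective contraception during therapy".
- Section 7.4 says "Participants will be asked to practice effective birth control while they are taking antiviral agents in this study".

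Peginterferon is given "subcutaneously (sq) weekly during weeks 9-48 of treatment" (section 5.1), and section 6.5 closes the treatment phase at week 48. Scheduled pregnancy tests also stop then (section 6.4 and Appendix I). No visible section asks for contraception after the last dose.

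On pharmacokinetics, section 5.3.1 states "The mean terminal half-life after subcutaneous dosing is 160 hours" and "Steady-state serum concentrations of peginterferon alfa-2a are reached within 5 to 8 weeks using once weekly dosing".

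On outcomes, section 7.4 adds: "The study will collect data on the outcomes of any pregnancies that occur in women who conceived while taking study medication". Section 7.5.1 groups pregnancy with events that "are not always serious by regulatory definition, these events must be handled as SAEs" and lists birth defects among the SAE criteria. Section 7.5.2 has events reported up to week 96 and followed until resolved or stable.

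**The concern.** Section 5.3.3 gives its reason for requiring contraception: the drug's potential to cause birth defects in humans has not been adequately studied, and there are no adequate controlled studies in pregnant women. That reason concerns fetal exposure to the drug, so it holds for as long as the drug is present and not only while it is being injected. The protocol supplies both the reason and the half-life but does not connect them.

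A woman who follows every visible instruction could stop contraception at week 48 and conceive while her peginterferon level is the same as at the end of any dosing week on treatment. SAE reporting would record that pregnancy. Contraception is the only step that would prevent it.

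**Working it through.** The protocol states no washout time, so there is no figure of its own to reproduce.

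**Inputs from the protocol**
- Half-life 160 h = 160/24 = 6.67 days = 160/168 = 0.952 weeks (5.3.1).
- Steady state reached in 5 to 8 weeks (5.3.1).
- Weekly dosing in weeks 9 to 48, so 40 doses starting at the week-8 visit, day 56 (5.1, 6.4).
- End of treatment and of contraception: week 48.

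**Assumptions**
- First-order, one-compartment elimination.
- Five half-lives count as washout, with a range of three to seven.

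**Step 1: last dose.** Day 56 + 39 × 7 = day 329 = week 47.0.

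**Step 2: share of the last-dose level remaining**, 0.5^(hours since last dose / 160):

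| Week | Hours since last dose | Share left |
|---|---|---|
| 48 | 168 | 48.3% |
| 49 | 336 | 23.3% |
| 50 | 504 | 11.3% |
| 51 | 672 | 5.4% |
| 52 | 840 | 2.6% |

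**Step 3: comparison with on-treatment levels.** At steady state on weekly dosing, trough/peak = 0.5^(168/160) = 0.483, which is the week-48 value above. Average/peak = (1 − 0.483)/(ln 2 × 168/160) = 0.710. The week-48 level is therefore 0.483/0.710 = 68% of the average on-treatment level. This step needs no washout rule.

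**Step 4: end of washout**, week 47 + k × 0.952:

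| Half-lives (k) | Days | Washout ends, week | Weeks after week 48 |
|---|---|---|---|
| 3 | 20.0 | 49.9 | 1.9 |
| 4 | 26.7 | 50.8 | 2.8 |
| 5 | 33.3 | 51.8 | 3.8 |
| 7 | 46.7 | 53.7 | 5.7 |

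**Step 5: sensitivity**
- Last dose at week 48 instead of 47: the gap is 4.8 weeks at five half-lives (2.9 at three, 6.7 at seven).
- The protocol gives no between-patient spread. At an assumed half-life of 120 h, five half-lives end at week 50.6 (gap 2.6 weeks). At 200 h they end at week 53.0 (gap 5.0 weeks).
- Steady-state time: under first-order kinetics, washout takes as long as build-up. Weeks 47 + 5 to 47 + 8 give weeks 52 to 55, a gap of 4 to 7 weeks. This is consistent with the half-life, since 5/0.952 = 5.25 half-lives (97.4% of plateau) and 8/0.952 = 8.4 half-lives (99.7%).

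**Step 6: early stopping**
- Both drugs stopped, last injection 0 to 7 days earlier: 33.3 to 26.3 days remain, or 4.8 to 3.8 weeks from the stop. Over three to seven half-lives the range is 13.0 to 46.7 days, or 1.9 to 6.7 weeks.
- Peginterferon alone stopped: entecavir continues to the end of the treatment period (7.5.4), and contraception continues with it. Washout is then covered if the last injection was by week 48 − 4.8 = 43.2.

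**The case against.** The strongest reply is that this is a consistent clinical choice whose consequences are small. Several parts of it stand.

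- **Five half-lives is a convention.** The protocol states no washout rule, and by week 50 only about 11% of the last-dose level is left. This stands, and it is why a range is given.
- **The trough argument holds only at week 48.** By week 49 the level is about half the usual trough (23.3/48.3). This stands too. The comparison shows that coverage ends too early; the length of the gap depends on the washout assumption.
- **The steady-state check is not independent evidence.** It expresses much the same half-life with a stricter cut-off. Agreed; it is a consistency check only.
- **Harm is not shown.** The monkey abortions in section 5.3.3 were at about 20 to 500 times the human weekly dose, and that section warns that interferon effects differ strongly between species. This stands. But the same uncertainty applies during treatment, when the protocol still requires contraception.
- **Pregnancies are captured.** They are handled as SAEs and reported to week 96, and there are visits at weeks 52 and 60. Outcome capture is therefore not the main gap, but it does not prevent conception.
- **Other documents may cover this.** The consent form and Manual of Operations could carry post-treatment advice. The finding is limited to the protocol text. Any longer instruction elsewhere would need to be aligned with 4.2, 5.3.3 and 7.4.
- **Few women are affected.** Only women of childbearing potential among the 40 participants are concerned, and their number is not given. This limits the scale but does not close the gap.

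**Conclusion.** The concern holds. The contraception rule ends while peginterferon is still at its on-treatment trough, about 68% of the average treatment level. The uncovered period after week 48 is about 4 weeks at five half-lives (about 2 at three, about 6 at seven). It is 4 to 7 weeks if the protocol's steady-state time is used as the guide. Women who stop both drugs early face a similar gap from the day they stop.

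The start of the gap rests on the protocol's half-life and dosing schedule, with first-order elimination assumed. Its length also rests on the assumed number of half-lives. This is a precautionary safety point that follows from the protocol's own reasoning; it is not evidence of harm, and it has no bearing on the efficacy estimate.

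**What to change.** In sections 4.2 (item 7), 5.3.3 and 7.4, require effective contraception until about 5 weeks after the last peginterferon dose or until the last study drug dose, whichever is later. Five weeks is 840/160 = 5.25 half-lives, which leaves about 2.6% of the last-dose level. Remind women of this at the week-48 visit, or at the visit where both drugs are stopped. For consistency, use the same window in the section 7.4 sentence on collecting pregnancy outcomes. A urine test at the existing week-52 visit is optional, and no week-60 test is needed.

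The cost is a wording change in three places and about 4 more weeks of contraception for women of childbearing potential. No visit or required test is added.

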7.5. Adverse events – definition and management

7.5.1. Definitions

An adverse event (AE) is any adverse change from the participant's baseline (pre-treatment) condition, including intercurrent illness which occurs during the course of the trial, after the consent form has been signed, whether the event is considered related to treatment or not.

The modified World Health Organization (WHO) grading system will be used for grading severity of AEs. For AEs not outlined in the modified WHO grading system, study specific definitions will be identified in the Manual of Operation (MOP).

A serious adverse event is an untoward medical occurrence that results in any of the following:

1. Death
2. Is life threatening (risk of death at the time of the event)
3. Requires in-patient hospitalization or prolongation of existing hospitalization
4. Results in persistent or significant disability/incapacity
5. Congenital abnormality or birth defect

Important medical events that do not result in one of the events listed above may be considered a serious adverse event when, based upon appropriate medical judgment, they may jeopardize the participant and may require medical or surgical intervention to prevent one of the outcomes listed above.

A serious adverse event which is unexpected and is related will require expedited reporting to the DCC and the NIDDK and appropriate oversight committees or entities.

Disease related outcomes, such as the following, will not be considered to be serious adverse

events:

1. Development of HCC
2. Hepatic decompensation

Although pregnancy, overdose, cancer (excluding HCC), and potential drug induced liver injury (DILI) are not always serious by regulatory definition, these events must be handled as SAEs.

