2.2 Primary endpoint

2.2.1 Safety: Adverse Events and Serious Adverse Events through the end of treatment and through the end of follow-up

2.2.2 Efficacy: HBeAg loss (lack of detectable HBeAg) AND HBV DNA $\leq 1,000$ IU/mL 48 weeks after stopping therapy.

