7.5.2. Data collection procedures for adverse events

Participants will be interviewed regarding medical conditions, medication changes, and symptoms that have occurred at each study visit. An Adverse Event form will be completed if any adverse event is reported. If the study coordinator or a study physician learns of any hospitalizations or other adverse events between study visits, an Adverse Event form will be completed. All adverse events and Serious Adverse Events from time of study entry (consent) up to the end of follow-up (week 96) will be reported to the DCC.

A Serious Adverse Event form will be completed for all adverse events rated as serious.

Participants will be followed for all ongoing unresolved adverse events until they are either resolved, or in the opinion of the study physician, the participant is medically stable.

A study physician will assess the relationship of each adverse event to the use of study drug, based on available information, using guidelines outlined in the MOP.

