8.1.1. Analysis of primary endpoints

The primary endpoints include safety, measured by the rate of adverse and Serious Adverse Events, and efficacy, defined as loss of HBeAg and HBV DNA $\leq 1,000$ IU/mL at the end of follow-up (week 96). That is, only participants achieving HBeAg loss and having HBV DNA ≤ 1000 IU/mL at the end of follow-up will be considered as achieving the primary efficacy endpoint.

Safety

Summaries of adverse events (number of adverse events, number and percentage of participants with at least one adverse event, and for each adverse event, rate per person-years) will be provided. Events will be summarized based on the date of onset for the event. A treatment emergent adverse event will be defined as an adverse event that begins on or after the date of first dose of study drug.

Summaries of the following are planned:

- all adverse events recorded between screening and first dose of study medication,
- all treatment emergent adverse events,
- all emergent and related adverse events,
- all treatment emergent renal adverse events,
- all treatment emergent and related renal adverse events
- combined Grade 2, 3 and 4 treatment emergent adverse events,
- combined Grade 2, 3 and 4 related treatment and emergent adverse events,
- combined Grade 3 and 4 treatment emergent adverse events,
- combined Grade 3 and 4 related treatment and emergent adverse events,
- all adverse events that caused permanent discontinuation of study drug,
- all adverse events that caused temporary interruption of study drug,
- all serious adverse events, and
- all serious and related adverse events.

We will provide 95% confidence intervals for the rate of adverse and serious adverse events.

Efficacy

The percentage of participants achieving the primary efficacy endpoint will be summarized with the point estimate and 95% confidence interval.

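### Section 7.5.1 exempts HCC and hepatic decompensation from SAE status even when they meet its own seriousness criteria, so a qualifying non-fatal case can be absent from the SAE rate in the primary safety endpoint

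*Combined protocol and SAP*

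**What the plan says.** - **Endpoint.** Section 2.2.1 defines the primary safety endpoint as "Adverse Events and Serious Adverse Events through the end of treatment and through the end of follow-up". Section 8.1.1 measures it by the rates of AEs and SAEs and adds: "We will provide 95% confidence intervals for the rate of adverse and serious adverse events".
- **Seriousness criteria.** Section 7.5.1 lists death, life-threatening events, disability and congenital abnormality, and this criterion: "Requires in-patient hospitalization or prolongation of existing hospitalization".
- **Exemption.** The same section continues: "Disease related outcomes, such as the following, will not be considered to be serious adverse" events, and names development of HCC and hepatic decompensation. The list is given by way of example, so it is open, and nothing brings back a case that meets a criterion. The next sentence again leaves HCC out of the cancers to be handled as SAEs.
- **Liver injury from drug.** That sentence also says that pregnancy, overdose, other cancers and "potential drug induced liver injury (DILI) are not always serious by regulatory definition, these events must be handled as SAEs".
- **Forms.** Under 7.5.2, if staff or a study physician "learns of any hospitalizations or other adverse events between study visits, an Adverse Event form will be completed". The SAE form is for events rated serious. Section 7.5.3 puts all deaths on the SAE form.
- **Summaries.** Section 8.1.1 plans, among others, all treatment-emergent AEs, graded AEs, "for each adverse event, rate per person-years" and "all adverse events that caused permanent discontinuation of study drug". Renal events have their own lines; HCC and decompensation do not.
- **Monitoring.** Section 9.1 gives the DSMB a cumulative AE summary every three months, overall and split into serious and non-serious.

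**The concern.** The SAE rate is half of the primary safety endpoint, and the exemption works by diagnosis, not by seriousness. A participant admitted to hospital with decompensation can meet a listed criterion and still not count as having an SAE.

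In this trial decompensation cannot be assumed to be purely a disease outcome. Section 5.3.3 names disease flares and worsening decompensation as peginterferon hazards, although in patients with decompensated cirrhosis, who are excluded here. Section 7.3.1 lists hepatitis flares under entecavir. Section 6.8 makes decompensation a reason to stop treatment, and 6.11 foresees it during ALT flares. Section 9.1 says the two drugs are well studied except in immune tolerant participants.

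At stake is whether someone who reads only the SAE table, or only the serious stratum of the DSMB summary, would see such an event.

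**Working it through.** **1. Which cases fall through.** Four conditions must hold together:

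- The case is non-fatal. Deaths go on the SAE form (7.5.3).
- It meets a 7.5.1 criterion such as hospitalization or threat to life. Otherwise it would not be an SAE under any reading.
- It is not handled as potential drug-induced liver injury. If it were, 7.5.1 would make it an SAE. That route depends on suspected cause, not on seriousness, and does not reach HCC.
- The participant has no other SAE. Otherwise the participant already counts in the SAE proportion, and only the count of SAE events is one short.

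**2. Where such a case appears.**

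| Output | Does it show the case? |
|---|---|
| SAE rate and 95% CI (8.1.1) | No |
| Serious stratum of DSMB summary (9.1) | No |
| Overall and non-serious parts of DSMB summary (9.1) | Yes |
| All-AE and graded summaries (8.1.1) | Yes, according to onset and grade |
| Per-event rate per person-years (8.1.1) | Yes |
| Permanent-discontinuation summary (8.1.1) | Only if it led to stopping drug, so only while on treatment |

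None of the summaries listed in 8.1.1 is defined to show that a non-SAE event met a seriousness criterion.

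**3. The plan's own interval method.** The only precision calculation is for efficacy (8.3): N = 40, Clopper-Pearson. The limits are the 0.025 quantile of Beta(x, n − x + 1) and the 0.975 quantile of Beta(x + 1, n − x). For 10/40 they are 0.127 and 0.412, width 0.285, which matches the tabled 0.29. The other three rows also reproduce. Section 8.1.1 names no method for the SAE interval; using the same one here is an assumption.

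**4. Size of one omitted participant.** The shift in the SAE proportion is 1/40 = 2.5 percentage points. To give a background, 5.3.3 cites 4%–5% SAEs in hepatitis B studies: 0.04 × 40 = 1.6 and 0.05 × 40 = 2.0 participants.

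| Other participants with an SAE (assumed) | Reported under the exemption | With the omitted case |
|---|---|---|
| 0 | 0/40 = 0% (0–8.8%) | 1/40 = 2.5% (0.1–13.2%) |
| 2 | 2/40 = 5.0% (0.6–16.9%) | 3/40 = 7.5% (1.6–20.4%) |

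For zero events the upper limit is 1 − 0.025^(1/40) = 0.088.

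**5. The same event in the AE half.** With full follow-up, person-time is at most 40 × 96 × 7 / 365.25 = 73.6 person-years. One event is 1/73.6 = 1.36 per 100 person-years, and the per-event AE rate would report it as such.

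**6. Likelihood.** The documents give no rate for HCC or decompensation in this population, so no probability is calculated. Entry excludes past or current decompensation (4.2), requires persistently low ALT, screens for HCC, and requires a biopsy with minimal disease above age 50 (4.1).

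**The case against.** The strongest reply is that this is a declared definition. The protocol says openly which disease-related outcomes are not SAEs, repeats the exclusion for HCC, and builds the endpoint on that definition. The SAE rate is then too low only against a different definition. This is a pilot with descriptive safety analysis: no test, stopping threshold or precision target hangs on the SAE rate, and stopping an individual's treatment for decompensation does not depend on SAE status.

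Much of this stands. The exemption may well be deliberate and can be kept. But the criteria that the omitted case meets are the plan's own, and no listed summary adds such cases back.

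Several stronger readings are tempting, and the documents do not support them:

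- *These events disappear from safety reporting.* They do not. They meet the AE definition, are reported through week 96, and in a study of 40 would be visible in the AE tables.
- *The single-arm design hides the omission.* A control arm under the same exemption would omit its cases too and would reveal nothing.
- *The liver-injury sentence flatly contradicts the exemption.* The exemption covers disease-related outcomes, and the next sentence requires even potential drug injury to be handled as an SAE. The natural reading is that a possibly drug-induced decompensation is an SAE. What remains is a boundary worth stating.
- *The seriousness of an exempt event goes unrecorded.* The AE form is not among the documents, and 7.5.2 calls for one when a hospitalization is learned of between visits. The form may already hold this information.

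The Manual of Operations, the DSMB Charter and the industry partners' SAE requirements cited in 7.5.3 are also unseen and may address the matter.

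**Conclusion.** The point holds in a narrow form. As written, 7.5.1 keeps a non-fatal HCC or decompensation that meets a seriousness criterion out of the SAE rate and CI, and out of the serious stratum of the DSMB summary. The exceptions are a case handled as potential drug-induced liver injury and a participant who already counts through another SAE.

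The effect runs in one direction, towards a lower SAE rate, and amounts to 2.5 percentage points per affected participant if 40 are treated. It is confined to the SAE figures; the AE figures are intact. If no such event occurs, nothing changes, and the entry criteria make an event unlikely.

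The intervals assume the Clopper-Pearson method, and the event counts are illustrations. A reader might infer that the primary safety result is likely to be wrong; the documents give no event rate that would support that. This is a minor improvement at low cost.

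Two boundaries remain unstated in the text: how the open exemption list relates to potential drug-induced liver injury, and whether a death from an exempt event, which goes on the SAE form, also counts in the SAE table.

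**What to change.** 1. In 8.1.1 and the DSMB reports, add a line for HCC and hepatic decompensation: number of participants, percentage, 95% CI, and how many met a 7.5.1 seriousness criterion.
2. Report the SAE rate with and without the events that met a criterion, and name the interval method.
3. Make sure the data collected identify which criterion, if any, an exempt event met. If the AE form already does so, no change is needed.
4. Add a clarifying sentence that reconciles the open exemption list in 7.5.1 with the potential liver-injury sentence there and with the all-deaths rule in 7.5.3, or cite the Manual of Operations, Charter or partner requirement that already does.

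The cost is one table line, a second SAE figure, at most one form field, and a sentence or two of text. The figure that includes these events may be slightly higher. Showing both keeps the exemption and preserves comparability with studies that also exempt disease-related outcomes.
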